- *Control Preferences Scale for Pediatrics (CPS-P)*¹¹³: The CPS-P will measure parent preferences for participation in treatment decision making pre-intervention and will be included in the survey given to 37 participating parent-patient dyads. Descriptive statistics will be calculated for quantitative data from this survey.
- *Hospital Anxiety and Depression Scale (HAD)*¹¹⁴: The HAD Scale will measure parental levels of depression and anxiety pre-intervention and will be included in the survey given to 37 participating parent-patient dyads. Descriptive statistics will be calculated for quantitative data from this survey.
- *Impact of Event Scale-Revised (IES-R)*¹¹⁵: The IES-R will measure parental levels of post-traumatic stress disorder pre-intervention and will be included in the survey given to 37 participating parent-patient dyads. Descriptive statistics will be calculated for quantitative data from this survey.

- *Trust in Physician Scale*¹¹⁶: The Trust in Physician Scale will measure parental levels of trust in the clinical team pre-intervention and will be included in the survey given to 37 participating parent-patient dyad. Descriptive statistics will be calculated for quantitative data from this survey.
- *Pediatric Family Satisfaction with Care in the Intensive Care Unit (PFS-ICU 24)*¹¹⁷: The PFS-ICU will measure parental satisfaction with care and medical decision-making (modified for parents/caregivers of critically ill children) pre-intervention and will be included in the survey given to 37 participating parent-patient dyads. Descriptive statistics will be calculated for quantitative data from this survey.
- *Communication Assessment Tool-Team (CAT-T)*¹¹⁸: The CAT-T, adapted to team environments, will measure parental perception of communication with the medical team pre-intervention and will be included in the survey given to 37 participating parent-patient dyads. Descriptive statistics will be calculated for quantitative data from this survey. This study will generate data that: a) is of substantial descriptive interest; b) will enable the evaluation of this population of CICU clinicians; c) will enable us to test the study's hypotheses; and d) will enable us to estimate the size and precision of the associations between the variables specified in the hypotheses.

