A sample size of 130 parent-patient dyads for the survey and 30 parent-patient dyads for the interview is based on using CONSORT recommendations for pilot study sample size calculations. We calculated the parent-patient dyad sample size by estimating the required sample size for the future stepped wedge study using the Hospital Anxiety and Depression Scale (HADS) as the primary outcome for parents, as HADS is a frequently used outcome in palliative care research with well-established psychometric properties.^{129,130} We will assume a one sided 80% CI for the effect size of 0.1 times the SD, to exclude the minimum clinically important difference if the null hypothesis is true.¹³¹ The minimally important difference is a change of 2 on the HADS scale. The estimated sample size for the main study would be 286. For the pilot study, we estimated the number of participants required as around 30% of the number required for the main Phase 3 trial therefore, we aim to enroll a total of 46 parent-patient dyads pre and post the intervention. In previous studies enrolling parents and children with serious illness, our approach-to-enrollment rate was above 50%. Assuming 45% or more of parent-patient dyads approached will enroll and there are 150 eligible patients per year, we will need to approach approximately 350 parent-patient dyads to enroll 130 evaluable parent-patient dyads for the survey and 30 evaluable parent-patient dyads for the interview prior to the intervention. We have allotted 24 months to enroll 46 evaluable parent-patient dyads for the survey and 20 evaluable parent-patient dyads for the interview pre-intervention.

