## Statistical Analysis Plan

Aim 2: Pilot test the co-design-adapted CICU TALC with CICU parents and clinicians to determine:

a) Acceptability of intervention: Hypothesis: Respondents will endorse above a critical threshold of acceptability on satisfaction instruments to 20 clinicians and 23 parents and in semi-structured interviews.

Analytic plan: A constructivist grounded theory approach will guide qualitative analysis of interview transcripts regarding acceptability of the intervention. Descriptive statistics will be calculated for quantitative data from the acceptability survey.

b) Feasibility of enrollment and data collection, and fidelity: Hypothesis: Feasibility will be defined by: i) 30% parental and 50% clinician enrollment and consent rates, and 80% subject retention, and attrition; ii) ability to collect outcomes data from 46 patients (CICU length of stay), from 46 parents and from 50% of eligible team members. and iii) intervention fidelity with 95% of enrolled parents and clinicians receiving parent-directed and team-directed interventions.

Analytic Plan: Data completeness and accuracy will be monitored. I will calculate descriptive summaries including means and standard deviations for continuous variables, and proportions for categorical variables. As appropriate for pilot trials, analyses will focus on estimating proportions of binary feasibility and fidelity endpoints and constructing 95% CIs. Analyses of parent-reported outcomes will primarily be descriptive. Means and standard deviations along with 95% confidence intervals will be calculated.

c) Impact of CICU TALC on CICU parent and team behavior in family meetings. Hypothesis: the intervention will increase parent speaking time by 60%, elicitation of parental concerns to 40%, and response to parental emotion by 30%. I will audio record 230 CICU family meetings occurring before CICU TALC is initiated and 230 after initiation and use quantitative methods to measure pre-vs-post differences in a) speaking time of parents and physicians; b) elicitation of parental concerns; and c) response to parental emotion.

Analytic Plan:

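### Section 6.4 gives two HADS targets for the parent sample, 0.1 SD and 2 points, that agree only if the SD is 20; no SD is stated and no pre/post HADS contrast is planned

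*Protocol*

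**What the plan says.** The last paragraph of Protocol section 6.4 explains the parent-patient dyad sample by reference to a future stepped-wedge trial, "using the Hospital Anxiety and Depression Scale (HADS) as the primary outcome for parents". The precision criterion is "We will assume a one sided 80% CI for the effect size of 0.1 times the SD, to exclude the minimum clinically important difference", with the condition "if the null hypothesis is true". The margin follows: "The minimally important difference is a change of 2 on the HADS scale". Then comes a total: "The estimated sample size for the main study would be 286". The pilot is set at "around 30% of the number required for the main Phase 3 trial", and the paragraph gives 46 dyads across the two phases. It also gives 130 for the survey. No SD for HADS appears anywhere.

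Other sections give different parent numbers:
- Section 3.3.2 stops recruitment at 100 evaluable dyads before the intervention and up to 30 after it.
- Section 8.5 expects 95 evaluable before and 30 after.
- Section 6.2 gives 37 for the pre-intervention HADS.
- Sections 3.1 and 3.1.1 allow up to 100 enrolled before and, in 3.1, up to 50 after.
- The SAP, Aim 2b, plans outcome data from 46 parents.

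On analysis, section 6.2 says "The HAD Scale will measure parental levels of depression and anxiety pre-intervention", summarised descriptively. The SAP says "Analyses of parent-reported outcomes will primarily be descriptive" and adds means, SDs and 95% confidence intervals. The contents list for the post-intervention parent survey (Appendix 11.15) also includes HADS.

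**The concern.** A precision-based sample size needs one margin, one SD and one confidence level. Section 6.4 gives the level and two margins, one in SD units and one in points, with no SD to link them. The reader cannot tell which margin the sample was meant to exclude, whether the sample does so, or how 286 was obtained.

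The criterion is about a difference between phases, yet neither document names a post-minus-pre HADS difference as an analysis. The quantity used to justify the sample is therefore not scheduled to be estimated. At stake is the stated rationale for the parent sample and the HADS inputs that the pilot hands to the later trial.

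**Working it through.** **Inputs.** One-sided 80% level, z = 0.8416 (6.4). True difference zero (6.4). Margin 0.1 SD or 2 points (6.4). Phase sizes as listed above. Dyads are recruited separately before and after the intervention, so I treat the phases as two independent groups with a common SD. The SD is not given; where one is needed I assume 4 to 10.

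**1. Reproducing 286 from the stated criterion.** The half-width in SD units is h = z × √(1/n₁ + 1/n₂). With equal groups and h = 0.1, the total is 4 × (0.8416/0.1)² = 283.3, so 284. With the t distribution the smallest size that meets 0.1 is 143 per group, or 286. The criterion at 0.1 SD therefore gives the printed number, but as the size of the comparison to which the interval applies.

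**2. A second route to 286.** For a two-arm comparison of 2 points at two-sided 5% and 80% power, n per arm = 2 × (1.960 + 0.8416)² × (SD/2)². With an assumed SD of 6 this is 2 × 7.849 × 9 = 141.3, so 142 per arm and 284 in all. The t-based calculation gives 286. So 286 is also an ordinary main-study size for 2 points, if the SD is 6. The documents state neither that SD nor a power and alpha for HADS.

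**3. Do the two margins agree?** 0.1 × SD = 2 requires SD = 20. At SDs of 4 to 10, 0.1 SD is 0.4 to 1.0 points, and 2 points is 0.50 to 0.20 SD.

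**4. Precision at the planned sizes.** The last column is 2/h (z), the largest SD at which 2 points is excluded when the observed difference is zero.

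| Pre + post | h, z | h, t | SD below which 2 points is excluded |
|---|---|---|---|
| 23 + 23 | 0.248 | 0.251 | 8.06 |
| 37 + 30 | 0.207 | 0.208 | 9.67 |
| 46 + 46 | 0.175 | 0.176 | 11.40 |
| 95 + 30 | 0.176 | 0.177 | 11.35 |
| 100 + 30 | 0.175 | 0.176 | 11.42 |
| 130 + 30 | 0.170 | 0.171 | 11.73 |
| 100 + 50 (enrolment ceiling) | 0.146 | 0.146 | 13.72 |

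Example: for 23 + 23, 0.8416 × √(2/23) = 0.248, and 2/0.248 = 8.06. The 130 + 30 row may count the post-intervention dyads twice, since 100 + 30 is already 130.

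No row reaches 0.10 SD. Against 2 points, every row suffices up to an SD of about 8. At SD 10, 23 + 23 and 37 + 30 fall short and the other rows suffice.

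**5. The 30% step.** 0.30 × 286 = 86. A total of 46 is 46/286 = 16%; 46 per phase (92) is 32%. This step does not settle which margin was meant.

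**6. The planned analysis.** Section 6.2 describes HADS before the intervention only. The SAP intervals are at 95% and are not tied to a pre/post difference. Neither document names the contrast or the one-sided 80% limit.

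**The case against.** The strongest reply is that section 6.4 does not promise that the pilot will exclude 0.1 SD. It says the interval is to exclude the minimally important difference, defines that as 2 points, and attaches 286 to the main study. On that reading the planned sample is adequate over most of the plausible SD range, and 286 is a sensible main-study size at an SD of 6. This stands. A reader might infer that the parent sample is too small, or that 286 is a pilot size printed under the wrong label. The documents show neither, because both depend on which margin was intended.

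A reader might also infer that the later trial is undersized about elevenfold, since 80% power for 0.1 SD at two-sided 5% needs 3,140. Section 6.4 does not support that. Its 80% for HADS is a confidence level; the power and alpha it states belong to the clinician endpoints. A stepped-wedge size would also depend on clustering and period effects, which are not given.

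It is also fair to say that parent outcomes will have intervals, since the SAP plans 95% ones, and that a sizing criterion need not be a reported analysis in a pilot. The primary endpoint is qualitative, HADS is one of several descriptive secondary measures, and no decision rule uses the interval. That limits the severity. It does not reconcile 0.1 SD with 2 points or supply the missing SD.

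**Conclusion.** The stated basis for the parent sample is inconsistent as written. The two margins agree only at an SD of 20, and no SD is given.

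- If 0.1 SD is the target, the pre/post comparison needs 284 (z) to 286 (t) dyads, and the planned sizes deliver half-widths of about 0.15 to 0.25 SD.
- If 2 points is the target, the sample may well suffice (SD below about 8 with 23 + 23, below about 11.4 with 100 + 30), and the 0.1 SD figure is wrong.

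The documents do not show which holds. Separately, no pre/post HADS contrast is specified although HADS is collected in both phases. These results assume independent phases, a common SD and no clustering. The point should be fixed; because HADS is a descriptive secondary measure here, it does not threaten the study's main purpose.

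**What to change.** In section 6.4:
- Remove or correct the 0.1 SD figure.
- State the margin in HADS points, with the SD actually assumed and its source. This review supplies no SD; the 6 used above only shows one route to 286.
- Say which calculation gives 286.
- Restate the precision at the evaluable goals. With 95 to 100 dyads before and 30 after, the one-sided 80% limit lies about 0.18 SD from the observed difference. At assumed SDs of 4 to 10 that is 0.176 × 4 = 0.7 to 0.176 × 10 = 1.8 points.
- Use one set of parent numbers, so that the precision statement matches sections 3.3.2, 6.2 and 8.5 and the SAP.

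In section 6.2 and the SAP, add the post-minus-pre HADS difference with its confidence interval, including the one-sided 80% limit and its direction, labelled as a planning estimate.

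The cost is a rewritten paragraph and one added line in each of two places. No extra dyads are needed. The downside is a stated precision less favourable than 0.1 SD.

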Clinician team members participating in an observed family meeting who will not undergo the CST (because they were not eligible, did not wish to participate in the study, or were not approached because sufficient clinicians were already enrolled) will be consented before the scheduled meeting to being audio or video recorded only in the observed family meeting. They will also be administered a survey at the end of the meeting. Clinicians not participating in the intervention will be enrolled for only the duration of their observed family meeting and may be enrolled more than one time during the course of the study.

Parent-patient Dyads Participating in the Survey or Interview Prior to Intervention

Potential subjects will be screened using the protocol inclusion and exclusion criteria. Parent-patient dyads will be recruited into the study in person or over the phone. The goal for enrollment will be 100 parent-patient dyads for the survey and up to 30 parent-patient dyads for the interview. 100 parent-patient dyads who are enrolled will be given an online survey on a laptop computer or via email to obtain baseline data assessing parental satisfaction, understanding, trust in the clinical team and emotional well-being. Medical record review of this group of patients will utilize EPIC and the PC⁴ database, but will not require patient or parent involvement. 30 enrolled parent-patient dyads will participate in an interview assessing their experiences in family meetings and their perspectives on communication with the clinical team.

Parent-patient Dyads Participating in the Survey or Interview After Intervention

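### Protocol 6.4 derives a total of 46 parent dyads as about 30% of 286, but 46 is 16%, and the pre-intervention targets in 3.3.2, 6.2, 6.4 and 8.5 do not agree

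*Protocol*

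**What the plan says.** Protocol 6.4 opens with 130 survey dyads and 30 interview dyads. For the future stepped-wedge trial it states: "We will assume a one sided 80% CI for the effect size of 0.1 times the SD". It gives 2 HADS points as the minimally important difference, and then: "The estimated sample size for the main study would be 286". The pilot is taken as "around 30% of the number required for the main Phase 3 trial therefore, we aim to enroll a total of 46 parent-patient dyads", with both phases counted in that total.

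On accrual, 6.4 assumes that at least 45% of those approached enrol and that "there are 150 eligible patients per year", and concludes that "we will need to approach approximately 350 parent-patient dyads to enroll 130 evaluable parent-patient dyads for the survey" plus 30 for the interview, in a sentence that ends by placing this before the intervention. The section closes: "We have allotted 24 months to enroll 46 evaluable parent-patient dyads for the survey", and "20 evaluable parent-patient dyads for the interview pre-intervention".

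Other sections give other numbers. Section 3.1 says "The goal for enrollment will be 100 parent-patient dyads for the survey". Sections 3.1.1 and 8.5 make 100 an upper limit on survey enrolment, and 8.5 expects 95 evaluable from it. Section 3.3.2 stops recruitment at 100 evaluable for the survey and 30 for the interview. Section 6.2 says that 37 dyads receive the survey, and repeats this for six instruments. SAP Aim 2b makes outcome data from 46 parents part of its definition of feasibility. SAP Aim 2a refers to 23 parents.

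**The concern.** The 46 is presented as a consequence of 286 and 30%, and it is not one. Section 6.4 also uses it in two ways: as a total over both phases, and as the pre-intervention survey number alone. The SAP carries 46 into a feasibility criterion without saying which is meant.

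Separately, a reader cannot tell which number completes pre-intervention recruitment. The one explicit stopping rule, in 3.3.2, conflicts with the enrolment cap and the expected loss in 8.5. What is at stake is whether the feasibility criterion and the end of recruitment can be judged without argument afterwards.

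**Working it through.** **1. The 30% step.** Inputs from protocol 6.4: 286, about 30%, 46.

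- 0.30 × 286 = 85.8, so 86. The stated 46 is not reproduced; the gap is 40.
- 46 / 286 = 16.1%.
- 46 / 0.30 = 153, the main-study size of which 46 would be 30%.
- Per phase: 46 + 46 = 92, and 92 / 286 = 32.2%. This is loosely about 30%, but it contradicts a total of 46.

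**2. Where 286 could come from.** No HADS SD, power or cluster input is given for it. Two routes fit.

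- Confidence-interval route, using the stated one-sided 80% and 0.1 SD: half-width = t(0.80) × √(2/n) in SD units. At n = 142 per group it is 0.10003; at n = 143 it is 0.0997. So 143 per group, 286 in total. The normal formula gives 4 × (0.8416/0.1)² = 283.3, or 142 per group and 284.
- Power route, using the stated 2 points with an assumed SD of 6, 80% power and two-sided 0.05: the t-test needs 142.2 per group, so 143 and 286 in total.

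**3. Where 46 could come from.** A one-sided 80% interval that excludes 2 points needs a total of 4 × (0.8416 × SD/2)². No SD is stated. Over assumed SDs of 4, 5, 6, 7 and 8 this is 11.3, 17.7, 25.5, 34.7 and 45.3. At SD 8 it rounds up to 23 + 23 = 46, which would also fit the SAP's 23 and 46. In that case the 30% is the error.

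**4. Pre-intervention targets side by side.**

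| Protocol section | Survey | Interview |
|---|---|---|
| 3.1 | 100 enrolled | up to 30 enrolled |
| 3.1.1 | up to 100 enrolled | up to 30 enrolled |
| 3.3.2, stopping rule | 100 evaluable | 30 evaluable |
| 6.2 | 37 surveyed | none given |
| 6.4, approach sentence | 130 evaluable | 30 evaluable |
| 6.4, last sentence | 46 evaluable | 20 evaluable |
| 8.5 | up to 100 enrolled, 95 evaluable | 30 enrolled, 23 evaluable |

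- The 130 equals 100 pre plus the 30 post in 3.3.2, so it is probably a two-phase total that has been labelled pre-intervention.
- At the 95% evaluable rate in 8.5, 100 evaluable needs 100 / 0.95 = 105.3, so 106 enrolled, which is above the cap.
- For the interview, 30 evaluable at 23/30 needs 30 / 0.767 = 39.1, so 40 enrolled against 30 planned.

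**5. Number approached.** This assumes that survey and interview dyads are separate and that every eligible patient is approached.

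- (130 + 30) / 0.45 = 356, which reproduces the approximate 350.
- (46 + 20) / 0.45 = 147, for the targets to which the 24 months are attached.
- (100 + 30) / 0.45 = 289; 289 / 150 × 12 = 23.1 months. This is 289 of the 300 eligible in 24 months, or 96%.

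**The case against.** Several defences hold, and they limit the point.

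- A reader might infer that 86 is the intended size and that the pilot is 40 dyads short. The documents do not support that. Step 3 shows a route to 46 that does not use the 30%, and the last sentence of 6.4 points to 92 in all.
- A reader might infer that 286 is really a confidence-interval size that has been mislabelled as a trial size. Both routes in step 2 give 286, each with one choice the protocol does not state (a t quantile, or an SD of 6). The supportable request is to state the derivation.
- A reader might infer an accrual shortfall, since 350 at 150 per year takes 28 months against 24. But 6.4 attaches the 24 months to 46 + 20, and 350 probably spans both phases. The 45% is also a floor, since 6.4 reports past rates above 50%.
- The 95 and 23 evaluable in 8.5 are ordinary attrition from 100 and 30 enrolled, and agree with 3.1 and 3.1.1. They conflict only with 3.3.2, where the targets are evaluable dyads, and with 6.2 and 6.4.
- A reader might infer a loss of precision for a pre-post difference in parent outcomes. The SAP specifies no such comparison: parent-reported outcomes are primarily descriptive, with means, SDs and 95% intervals.

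None of this rescues the step from 30% to 46, the two uses of 46, or the conflict among 3.3.2, 6.2, 6.4 and 8.5.

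**Conclusion.** The derivation in 6.4 is wrong as written: 46 is 16% of 286, not about 30%. Which of the three numbers is at fault cannot be settled from the documents. The pre-intervention targets conflict, and the 3.3.2 survey stopping rule can be met within the cap of 100 only if no enrolled dyad is lost.

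The consequence is limited to documentation and to judging feasibility. The primary endpoint is qualitative, parent outcomes are descriptive, and the survey targets in 3.3.2 and 8.5 total 125 to 130 over both phases (95 or 100 pre, plus 30 post), above both 46 and 86. The meaning of 46 still matters for the SAP: as a total it is well within those targets, but as a per-phase threshold it exceeds the 30 evaluable dyads at which post-intervention recruitment stops. The arithmetic on 46 needs no assumption. The possible origins of 286 and 46 rest on the assumed SDs shown.

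**What to change.** - **Protocol 6.4, derivation.** State the method and inputs behind 286. Restate or delete the step from 30% to 46, and say whether 46 is a total or per phase. Do not substitute 86 by default.
- **Protocol 3.3.2, 6.2 and 6.4, targets.** Replace the 37 in 6.2, the 46/20 and the pre-intervention 130/30 in 6.4, and the evaluable counts in the 3.3.2 pre-intervention stopping rule with one set that respects the cap. The 8.5 set would serve: up to 100 enrolled and about 95 evaluable for the pre survey, 30 enrolled and 23 evaluable for the pre interview, and 30 evaluable post from up to 50 enrolled.
- **Protocol 6.4, accrual.** Restate the number approached and the months for the targets kept. With 100 + 30 pre-intervention dyads at 45%, that is about 289 approached and about 23 of the 24 months, which leaves almost no slack and should be acknowledged.
- **SAP Aim 2b.** Add one sentence saying whether 46 parents is a total or a per-phase threshold.

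The cost is text edits, with no added participants if the cap is kept.

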Parent-patient Dyads Participating in the Survey or Interview Prior to Intervention: We will identify via medical record screening patients who have been admitted to the CICU for at least 7 days and are expected to stay for at least another 7 days and whose parents are therefore eligible for participation in a complex care family meeting. Parent-patient dyads will be approached in person by a member of the research team to consent to participate in the study or will be called to determine when they will next be present in the CICU for further discussion of the study. Up to 100 parent-patient dyads for the survey and 30 parent-patient dyads for the interview will be consented and enrolled with the expectation that we will achieve 95 evaluable parent-patient dyads for surveys and 23 evaluable parent-patient dyads for interviews.

Parent-patient Dyads Participating in the Survey or Interview After Intervention: We will identify via medical record screening patients who have been admitted to the CICU for at least 7 days and are expected to stay for at least another 7 days, or the patient has already been admitted to the CICU 14 days and whose parents are therefore eligible for participation in a complex care family meeting. Parent-patient dyads will be approached in person, over the phone or via e-mail by a member of the research team to consent to participate in the study or will be called to determine when they will next be present in the CICU for further discussion of the study. Up to 50 parent-patient dyads will be enrolled for, with a goal of 30 evaluable patient-parent dyads for the survey. Up to 25 parent-patient dyads (of the 50 enrolled for the survey) will be invited to be interviewed in the post-intervention, with a goal of 15 evaluable parent-patient dyads.

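### Section 6.4 states two different pre-intervention dyad targets, and no target in the protocol fits both its 350 approaches and its 24-month window

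*Protocol*

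**What the plan says.** The last paragraph of protocol section 6.4 projects parent-patient accrual. It reports a past approach-to-enrolment rate above 50% and then plans more cautiously: "Assuming 45% or more of parent-patient dyads approached will enroll". It continues that "there are 150 eligible patients per year, we will need to approach approximately 350 parent-patient dyads" in order "to enroll 130 evaluable parent-patient dyads for the survey and 30 evaluable parent-patient dyads for the interview prior to the intervention". No accrual period is given for that target.

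The next sentence gives a period for a different target: "We have allotted 24 months to enroll 46 evaluable parent-patient dyads for the survey", together with 20 for the interview, also labelled pre-intervention. A few lines earlier, 46 is the total for the pre and post phases together.

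Other sections give further pre-intervention figures:

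- Section 3.3.2 stops recruitment at 100 evaluable survey dyads and 30 evaluable interview dyads. It sets a separate post-intervention survey target of up to 30 evaluable.
- Section 8.5 enrols up to 100 for the survey and 30 for the interview, and expects that "we will achieve 95 evaluable parent-patient dyads for surveys and 23 evaluable parent-patient dyads for interviews".

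**The concern.** Section 6.4 is where a reader checks whether the baseline parent sample can be collected in the time available. It gives an approach count for one target and a time window for another, and both targets are described as pre-intervention. Neither target agrees with 3.3.2 or 8.5, so the reader cannot tell which number of dyads the 350 and the 24 months are meant to deliver.

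The text also moves from dyads approached to evaluable dyads using the enrolment rate alone, although 8.5 expects some enrolled dyads not to be evaluable.

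The stakes are mainly in planning. Under 3.1.4 the training follows the pre-intervention phase, so a window that does not match the target means either a smaller baseline sample or a longer pre-period. Enrolment is also a feasibility outcome in protocol 6.2 and in SAP Aim 2b, and the projection it will be read against should be coherent.

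**Working it through.** **Inputs.** From 6.4: enrolment 45% or more, 150 eligible per year, about 350 approaches, targets 130 + 30 and 46 + 20, and a 24-month window. From 3.3.2: 100 + 30 evaluable. From 8.5: 100 + 30 enrolled giving 95 + 23 evaluable.

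**Formulas.** Approaches = dyads to enrol / enrolment rate. Months = approaches / 150 × 12. Both assume that every eligible dyad is approached, and that survey and interview dyads are different people. Table 1 and the consent text in 8.6 treat them as separate groups before the intervention.

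**The plan's own figure.** (130 + 30) / 0.45 = 355.6, about 356, which is within 2% of the stated 350. In reverse, 350 × 0.45 = 157.5. So the 350 is the sum of the two groups divided by 45%, with every enrolled dyad counted as evaluable.

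**Supply in the window.** 2 × 150 = 300 eligible dyads, against 350 to be approached. Approaching 350 takes 350 / 150 × 12 = 28.0 months.

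**Each printed target, counted as dyads enrolled:**

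| Target | To enrol | Approaches at 45% | Months | Approaches at 50% | Months |
|---|---|---|---|---|---|
| 6.4: 130 + 30 | 160 | 356 | 28.4 | 320 | 25.6 |
| 6.4: 46 + 20 | 66 | 147 | 11.7 | 132 | 10.6 |
| 8.5: 100 + 30 | 130 | 289 | 23.1 | 260 | 20.8 |

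The 130 + 30 target fits the 350 but not 24 months. The 100 + 30 target fits 24 months but not the 350. The 46 + 20 target needs less than half of either.

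**Yield from 300 eligible dyads.** At 45%: 300 × 0.45 = 135 enrolled, 25 short of 160. At 50%: 150. Reaching 160 needs 160 / 300 = 53.3%.

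**Enrolled to evaluable, using 8.5's ratios (95/100 and 23/30):**

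- 100 + 30 enrolled gives 95 + 23 = 118 evaluable, 12 fewer than 3.3.2's stopping count of 130.
- 100 + 30 evaluable needs 100/0.95 + 30/(23/30) = 105.3 + 39.1 = 144.4 enrolled. That is 321 approaches and 25.7 months at 45%, or 289 and 23.1 months at 50%.
- 130 + 30 evaluable needs 136.8 + 39.1 = 176 enrolled (rounded). That is 391 approaches and 31.3 months at 45%, or 352 and 28.2 months at 50%.

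The last figure is close to 350, but it rests on a 50% rate that 6.4 does not use for its projection, and it still exceeds 300.

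**The case against.** The strongest reply is that 6.4 never attaches the 24 months to 160 dyads. It attaches the window to 46 + 20, which needs about 12 months; allowing more time than the minimum is slack, not an error. A reader might infer from 350 against 300 that the 160 dyads cannot be reached. The documents do not support that. The 45% is a floor, the past rate is given as above 50%, and 53.3% of 300 would give 160 enrolled. Patients already in the unit at the start would add to the 300. This reply stands, and it limits what can be claimed.

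A second reply is that 130 may be 100 pre-intervention plus 30 post-intervention survey dyads. Those are 3.3.2's figures, and 6.4 opens by giving 130 + 30 without naming a phase. The 350 approaches would then span both phases, and the pre-phase need would be 130 dyads, 289 approaches and 23.1 months, which fits 24. This is plausible, but it is an inference. It would mean that the phrase placing the target before the intervention is misplaced or covers only the interviews. It also leaves the 46 + 20 sentence at odds with 3.3.2 and 8.5.

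Third, the 350 is approximate and reproduces. The gap between 157.5 and 160 is rounding and is not a fault. What remains is the missing allowance for non-evaluable dyads, and even that relies on carrying 8.5's ratios over to other targets.

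Finally, pre-intervention recruitment stops on counts, and the parent survey outcomes are mainly descriptive, so no hypothesis test turns on the 24 months. That is correct and keeps the consequence modest.

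**Conclusion.** The accrual paragraph needs correcting. It prints two pre-intervention targets, 160 and 66 dyads, in consecutive sentences, and neither matches 3.3.2 or 8.5. At the 45% planning rate no printed target fits both the 350 approaches and the 24 months. If the 130 + 30 target is the intended one, it is not reached in 24 months at that rate: 135 enrolled against 160, or about 28 months instead of 24. If 46 + 20 is intended, both the approach count and the window are more than twice what is needed. If 100 + 30 enrolled is intended, the window fits but the 350 does not.

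Separately, enrolling 8.5's 100 + 30 would not satisfy 3.3.2's stopping count, because 8.5 itself expects 118 evaluable and not 130.

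These results assume 150 eligible per year, all of them approached, no initial stock of patients, and separate survey and interview groups. If interview dyads could be drawn from the survey group, 130 / 0.45 = 289 approaches would fit within 300, but the pre-intervention procedures do not describe that.

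**What to change.** State one pre-intervention target in 6.4 and make 3.3.2 and 8.5 agree with it, saying whether the numbers are enrolled or evaluable. Say whether 130 combines pre- and post-intervention survey dyads. Then set out eligible, approached, enrolled, evaluable and months in that order, with a range for enrolment such as 45% to 50%.

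Two worked options from the protocol's own figures:

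- 100 + 30 enrolled (95 + 23 evaluable): about 260 to 289 approaches and 21 to 23 months. Section 3.3.2 would then stop at 95 + 23 evaluable, or at 100 + 30 enrolled.
- 100 + 30 evaluable, as 3.3.2 now reads: about 144 enrolled, 289 to 321 approaches and 23 to 26 months. The enrolment limits in 8.5 would have to rise.

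Remove or correct the 350 figure and the sentence allotting 24 months to 46 + 20 to match the chosen target. The cost is a few sentences in three sections and no new procedures. The stated expected yield may become slightly less favourable.
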